### 12.5.4 General Statistical Considerations

All collected study data will be presented in subject data listings. Statistical analyses will be performed using SAS® for Windows, version 9.3 or later. Descriptive statistics (n, mean, standard deviation, median, minimum and maximum) will be calculated by treatment group for continuous variables. Frequencies and percentages will be presented by treatment group for categorical variables.

## **12.6 Analysis Populations**

### **12.6.1 Intent-to-Treat Population**

The Intent-to-Treat (ITT) population is defined as all randomized subjects. The Intent-to-Treat population will be the primary population for the analysis of the primary and secondary endpoints.

### **12.6.2 Per Protocol Population**

The Per Protocol (PP) population is defined as all randomized subjects who were not associated with a major protocol violation.

### **12.6.3 Safety Population**

The Safety population is defined as any subject receiving the device/treatment. This population will be used for the analysis of safety parameters. This population includes the subjects from both Parts I and II of the study.

## **12.7 Statistical Methods**

A SAP will be developed and approved before the database is locked. The SAP will present the detailed statistical methodology to be used in analyzing the efficacy and safety data from this study. No inferential statistics will be performed on the baseline and safety data summaries.

### **12.7.1 Subject Disposition**

The disposition of all subjects who sign an ICF will be provided. The numbers of subjects screened, randomized, completed, and discontinued during the study, as well as the reasons for all post-randomization discontinuations will be summarized by device/treatment group. Disposition and reason for study discontinuation will also be provided as a by-subject listing.

### **12.7.2 Demographic and Baseline Characteristics**

Demographics and baseline characteristics (i.e., medical history, AP/Lateral/ Merchant/ posteroanterior radiograph View, etc.) will be summarized by device/treatment group using appropriate descriptive statistics and/or presented as by-subject listing on the safety population.

### **12.7.3 Protocol Deviations**

The deviations occurring during the clinical study will be summarized and/or presented as/by-subject listing.

### **12.7.4 Prior and Concomitant Medications**

All prior and concomitant medications recorded in the Case Report Form will be coded using the most recent version of WHO Drug dictionary. Descriptive summaries, by device/treatment group, will be prepared using the coded term. All prior and concomitant medications recorded in the Case Report Form will be listed.

### **12.7.5 Efficacy Analyses**

#### ***12.7.5.1 Primary Analysis***

##### Primary Endpoint:

The primary analysis will be conducted on the Intent-to-treat (ITT) population. The change in Knee and Osteoarthritis Outcomes Scores (KOOS) from baseline will be compared between the device/treatment groups using Repeated Measures Analysis of Covariance.

##### Secondary Endpoints:

The secondary endpoints will be analyzed using Analysis of Covariance (ANCOVA) models, or logit model to assess the differences between the two device/treatment groups depending on the nature of the endpoint. The Baseline KOOS will be used as Covariates.

- Clinical Endpoints

- Change in International Knee Documentation Committee (IKDC) Subjective Knee Evaluation Form scores from baseline
- Change in International Knee Documentation Committee (IKDC) Knee Examination Form scores from baseline
- Change in KOOS scores from baseline at Weeks 6, 12, 24, 36 and 104
- Change in Visual Analogue Scale (VAS) scores from baseline
- Change in SF-12 scores from baseline
- Change in the EQ-5D-5L scores from baseline
- Subject Satisfaction at Weeks 52 and 104
- Imaging Endpoints
  - MRI assessments at Day 10, Weeks 52 and 104
  - ICRS grade of chondral lesion at Day 10, Weeks 52 and 104

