#### 4. TABLE 3: STUDY FLOWCHART AND FOLLOW-UP ASSESSMENTS

Procedure	Screening/ Baseline	Surgery	Post-Operative Follow-up Evaluation						
	Visit 1	Visit 2	Visit 3	Visit 4	Visit 5	Visit 6	Visit 7	Visit 8	Visit 9
	Day -21 to -1	Day 0	Day 10 ±3 Days	Wk 6 ± 5 Days	Wk 12 ± 7 Days	Wk 24 ± 14 Days	Wk 36 ±14 Days	Wk 52 ±28 Days	Wk 104 ±56 Days
Informed Consent	X 								
Medical History & Demographics	X								
Subject Eligibility Verification	X	X							
Physical Assessment - Knee	X		X	X	X	X	X	X	X
Magnetic Resonance Imaging (MRI)	X 		X					X	X
Weight bearing AP / Lateral / Merchant View	X								
Weight-bearing posteroanterior radiograph	X								
Standing Long Leg Alignment	X							X	
International Cartilage Repair Society classification (ICRS)		X 	X 					X 	X 
International Knee Documentation Committee (IKDC) 	X			X 	X	X	X	X	X
Visual Analogue Scale (VAS), knee pain	X		X	X	X	X	X	X	X
Knee Injury and Osteoarthritis Outcome Score (KOOS)	X			X	X	X	X	X	X
SF-12	X			X	X	X	X	X	X
EQ-5D-5L	X		X	X	X	X	X	X	X
Subject Satisfaction								X	X

Adverse Events		X	X	X	X	X	X	X	X
Post-operative Rehabilitation 			X	X					
Concomitant Medications	X		X	X	X	X	X	X	X
Protocol Deviations	X	X	X	X	X	X	X	X	X

 Must occur prior to any study-specific procedures

 MRI must occur within 9 months of enrollment into this study confirming presence of a medial femoral chondral lesion and medial meniscal tear requiring a partial meniscectomy

 International Cartilage Repair Society (ICRS) classification will be used for intra-operative arthroscopic confirmation of the lesion grade

 International Cartilage Repair Society (ICRS) classification will be used for determination of lesion grade by MRI

 International Knee Documentation Committee (IKDC) Subject Knee Evaluation and Knee Examination Forms will be used

 IKDC Knee Examination Form - Subject dependent

 Post-operative Rehabilitation per Investigator standard of care

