### **10.1 Inclusion Criteria**

Subjects **MUST** meet **ALL** of the following criteria to be included in the study:

1. Given written informed consent on the IRB/REB approved Consent Form specific to the study, prior to study participation
2. Is male or non pregnant female  $\geq$  eighteen (18) years of age
3. MRI within 9 months of enrollment into this study confirming presence of a medial femoral chondral lesion and medial meniscal tear requiring a partial meniscectomy (as determined by the Investigator)
4. Must present with pain in the index knee of moderate or severe ( $> 30$  mm) as measured by the VAS
5. Must be able to understand English (written and oral)
6. Must be available to come to all study related visits and is physically and mentally willing and able to comply with all post-operative evaluations
7. Must be in general good health (as determined by the Investigator) based on screening assessments and medical history

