## 11.3 Visit Summary

### 11.3.1 Visit 1: Screening/Baseline (days -21 to -1)

All potential subjects screened for eligibility will be listed on the Screening and Enrollment Log. The Screening and Enrollment Log will document the date of screening, the results of screening, and the primary reason for excluding the subject (e.g., does not satisfy eligibility criteria or subject declined).

If all inclusion criteria and no exclusion criteria are met and the eligible subject agrees to participate in the study, he/she will be required to sign an IRB/REB approved ICF. After signing the ICF, each subject will have a knee physical assessment and study-related information will be collected.

The assessments to be performed at Visit 1 include, but are not limited to:

- Confirm written informed consent, prior to any screening procedures
- Inclusion/exclusion criteria
- Demographics (e.g., age, sex, work status, nicotine use)
- Concomitant medication, if applicable
- Medical and surgical history
- Physical Assessment – Knee
- IKDC Knee Examination Form
- Mechanism of injury
- Screening number assignment
- Confirm Visit 2 (surgery) scheduled within 1-21 days after screening

Imaging Assessment:

Pre-operative imaging include:

- Weight-bearing Anterior / Posterior
- Weight-bearing Lateral
- Merchant
- Weight-bearing posteroanterior radiograph
- Standing Long Leg Alignment
- MRI (within 9 months of enrollment into this study )

Subject self-reported questionnaires:

Subjects will be asked to complete the following questionnaires:

- KOOS
- IKDC Subjective Knee Evaluation Form
- SF-12
- EQ-5D-5L
- VAS, knee pain

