### **12.3 Sample Size Determination, Power calculation, and Rationale**

[figure not shown]
This study will be conducted in a two parts. There is no power calculation for the Part I study. In the Part II study subjects will be randomized to one of the two treatment groups in a 1:1 ratio.

A total of 82 subjects (41 in the study device group and 41 in the control device group) will be randomized in an effort to assure that seventy (70) subjects (i.e., 35 subjects per group) complete the study.

PASS version 2011, is used for this sample size and power calculation. The requirement of 70 subjects (35 active and 35 control) is based on achieving 80% statistical power to detect a non-inferiority margin difference of 8 points between the two groups (10). For the same 80% statistical power, and significance level (alpha) of 0.05 two-sided test; one may choose different number of subjects depending on the expected and observed KOOS score and the acceptance of the non-inferiority delta. These are depicted in Figure 12-1 below.

The discontinuation rate is predicted to be no more than 15%. To accommodate the potential discontinuations, 82 randomized subjects (41 in the study device group and 41 in the control device) are needed for this study.

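### Five of the nine secondary endpoints are adjusted for baseline KOOS instead of their own Visit 1 baseline, which costs some precision

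*Protocol*

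**What the plan says.** Protocol section 12.7.5.1, under Secondary Endpoints, sets the model: "The secondary endpoints will be analyzed using Analysis of Covariance (ANCOVA) models, or logit model to assess the differences between the two device/treatment groups", with the choice depending on the type of endpoint. It then names the covariate for the whole list: "The Baseline KOOS will be used as Covariates".

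Nine endpoints follow, seven clinical and two imaging. Five are changes from baseline in an instrument other than KOOS:

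- IKDC Subjective ("Change in International Knee Documentation Committee (IKDC) Subjective Knee Evaluation Form scores from baseline")
- IKDC Knee Examination
- pain VAS ("Change in Visual Analogue Scale (VAS) scores from baseline")
- SF-12
- EQ-5D-5L

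All five have a Visit 1 value. The flowchart in section 4 marks them at Screening/Baseline (for pain, the row "Visual Analogue Scale (VAS), knee pain"). Section 11.3.1 lists the four questionnaires, among them "IKDC Subjective Knee Evaluation Form", and separately the IKDC examination form. Nowhere does the protocol name any of these values as a covariate.

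**The concern.** A change score subtracts the endpoint's own baseline with a coefficient fixed at 1. ANCOVA on that baseline estimates the coefficient instead, and this is where its precision comes from. If the model holds only baseline KOOS, it recovers just the part of the own baseline that KOOS shares.

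Two things are at stake for the five endpoints. The standard error is larger than it needs to be in a trial with "35 subjects per group" expected to complete (section 12.3). And if the arms differ by chance in, say, baseline SF-12, part of that difference stays in the estimated treatment effect.

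Four endpoints are outside the point. For KOOS at other weeks, baseline KOOS is the own baseline. Subject Satisfaction has no baseline. The MRI assessments and ICRS grade are not defined as changes from baseline.

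**Working it through.** **Inputs from the protocol.** 35 completers per arm (section 12.3), consistent with 82 randomised and 15% discontinuation: 82 × 0.85 = 69.7. The protocol gives no figure for the effect of the covariate choice, so there is none to reproduce.

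**Inputs assumed.** The text gives no SDs or correlations. Set the follow-up SD to 1 and let:

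- s = baseline SD divided by follow-up SD (1.0, 0.8, 0.6)
- ρ = correlation of own baseline with follow-up (0.3, 0.5, 0.7)
- a = correlation of baseline KOOS with own baseline (0.3, 0.5, 0.7)

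Baseline KOOS is taken to relate to follow-up only through the own baseline. Scores are continuous and analysed by linear ANCOVA.

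**Residual variance of the change score.**

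- Own baseline in the model: 1 − ρ²
- Baseline KOOS only: 1 + s² − 2ρs − a²(ρ − s)²
- Ratio of the second to the first: R = 1 + (1 − a²)(s − ρ)² / (1 − ρ²)

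With ρ = a = 0.5:

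- s = 1.0: 1 + 0.75 × 0.25 / 0.75 = 1.25
- s = 0.8: 1 + 0.75 × 0.09 / 0.75 = 1.09
- s = 0.6: 1 + 0.75 × 0.01 / 0.75 = 1.01

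| s | lowest R on the grid | R at ρ = a = 0.5 | highest R on the grid | completers lost out of 70, at 0.5 |
|---|---|---|---|---|
| 1.0 | 1.09 | 1.25 | 1.49 | 70 − 70/1.25 = 14 |
| 0.8 | 1.01 | 1.09 | 1.25 | 70 − 70/1.09 ≈ 6 |
| 0.6 | 1.01 | 1.01 | 1.09 | 70 − 70/1.01 ≈ 1 |

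The highest values all come from ρ = a = 0.3. R is exactly 1 when ρ = s.

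**Power, for scale only** (no secondary endpoint has a power target). Take an effect with 80% power at two-sided 0.05 under own-baseline adjustment. Under KOOS-only adjustment its power is Φ{(1.96 + 0.84)/√R − 1.96}, which is about 71%, 77% and 80% for R = 1.25, 1.09 and 1.01.

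**Chance imbalance.** The fraction of an own-baseline imbalance left in the estimate is |ρ/s − 1|(1 − a²).

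- s = 1.0: from 0.3 × 0.51 = 0.15 to 0.7 × 0.91 = 0.64
- s = 0.8: from 0.125 × 0.51 = 0.06 to 0.625 × 0.91 = 0.57

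A typical imbalance is s√(2/35) = 0.239s. The typical shift is therefore 0.04 to 0.15 follow-up SD at s = 1.0, and 0.01 to 0.11 at s = 0.8.

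**Checks.** Simulation of 15,000 trials with 35 per arm gave 1.26, 1.09 and 1.01 for the three middle cases and 1.46 for the corner ρ = a = 0.3, s = 1. Mean estimates were within 0.005 of zero. A separate simulation of 4,000 trials gave 1.28 for ρ = a = 0.5, s = 1. When baseline KOOS was also allowed to predict follow-up directly (equal SDs), the ratio was 1.09 to 1.51 in the cases tried. Own baseline plus KOOS against own baseline alone gave 1.01 to 1.02.

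**The case against.** The best case for the plan has four parts.

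- **The covariate list may not be closed.** Section 12 calls itself brief and defers detail to the SAP, and the sentence on KOOS does not say that nothing else will be used. The SAP may indeed add covariates. But the protocol is not silent here: it names one specific covariate for the whole list. A SAP that follows it inherits the weakness, and a SAP that uses own baselines goes beyond the protocol text.
- **Own baseline is already subtracted.** This is true. The loss is only the gap between a coefficient of 1 and the fitted slope, and it disappears when ρ equals s. At that point KOOS could even be the more useful covariate if it carries separate information on follow-up, which is a reason to keep it in the model.
- **The size is assumed, and the upper corner is one extreme.** This stands. IKDC Subjective overlaps KOOS in content, so a correlation near 0.9 is conceivable; at equal SDs the ratio is then only 1.03 to 1.10. For VAS, the entry rule "Must present with pain in the index knee of moderate or severe" (> 30 mm, section 10.1) may shrink the baseline SD, which points to the low end.
- **The algebra is for linear models.** This stands too. If the IKDC Knee Examination goes to the logit model, the variance ratios do not apply, and the covariate choice also changes what the coefficient estimates. There the argument is qualitative.

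None of this shows that adjusting for KOOS alone is generally as good as using a baseline the trial already collects.

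**Conclusion.** The concern holds and is minor. Section 12.7.5.1 pairs five change scores with another instrument's baseline although their own baselines are available. Under linear ANCOVA no bias results over randomisations. The cost is a variance roughly 1.01 to 1.49 times what own-baseline adjustment would give, with middle values of 1.25, 1.09 and 1.01 depending on the SD ratio, and incomplete removal of chance imbalance.

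The direction is well supported. The size is not known, because it depends on assumed correlations and SD ratios and on KOOS acting only through the own baseline. The primary KOOS comparison at Week 52 and the sample size do not change.

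**What to change.** Replace the covariate sentence in section 12.7.5.1 with wording such as:

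> Baseline KOOS will be a covariate in every secondary model. The changes in IKDC Subjective, IKDC Knee Examination, VAS, SF-12 and EQ-5D-5L will also be adjusted for the Visit 1 value of the same score that is analysed.

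Referring to the same score settles which value applies where an instrument yields more than one, as EQ-5D-5L does. Fixing KOOS in every model keeps a defined covariate for Satisfaction, MRI and ICRS, and leaves none optional. The SAP should carry the same wording.

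The cost is one sentence. All five baselines are already collected. Keeping KOOS beside the own baseline adds about 1.5% to the variance with 70 completers under the assumptions above.

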#### ***12.7.5.2 Supportive Analysis***

To assess the consistency of the Primary Analysis results, supportive analysis will be conducted using the Per Protocol (PP) population. Statistical methodology for the supportive analyses will be the same as that of the primary analysis, with the exception of the analysis population used.

#### **12.7.6 Safety Analyses**

The Safety population will be used for the analysis of safety outcomes. All safety assessments will be tabulated and no hypothesis testing will be conducted in this analysis. For continuous variables data will be summarized by device/treatment group using n, mean, standard deviation, median, minimum and maximum values. For categorical variables data will be summarized by device/treatment group using frequency and percentage.

### ***12.7.6.1 Adverse Events / Adverse Device Effects***

Adverse Events will be coded using most recent version of MedDRA. Treatment Emergent AE's (TEAE) are defined as events with an onset on or after the first randomized treatment. TEAEs will be summarized by treatment group, System Organ Class, and preferred term. The following TEAE summaries will be provided:

- TEAEs by severity grade
- TEAEs by relationship to study device.

In addition, separate summaries of Serious Adverse Events will also be presented. The total number of subjects with at least one AE/ADE and the number of AEs/ADEs will be derived. If more than one AE/ADE with the same preferred term occurs within a subject during the study period, they will be counted only once for that subject using the worst reported severity and causal relationship to the intervention. AEs/ADEs will also be tabulated versus worst severity and worst relationship to the intervention.

Symptoms, AEs recorded before administration of intervention will only be presented in listings.

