## 6. OVERVIEW OF INVESTIGATIONAL PLAN

This is a prospective, double blinded, multi-center, randomized, controlled study with enrollment of 82 randomized subjects at up to 13 study sites. Study duration will be until the last subject enrolled reaches 104 weeks post-operative.

Subjects requiring arthroscopic treatment of a single medial femoral chondral lesion plus partial medial meniscectomy procedure will be randomly assigned to one of the following device groups. The assignment will be based on a 1:1 ratio (Group I: Group II):

- Group I: Radiofrequency-Based debridement using the Quantum 2 Controller plus Paragon T2 ICW Wand or the WEREWOLF Controller plus FLOW 50 Wand (**study devices**)
- Group II: Mechanical Debridement (**control device**)

Study visits will be conducted at the following time points:

- **Visit 1:** Screening/Baseline (Day -21 to -1)

- **Visit 2:** Day 0- Surgery
- **Visit 3:** Day 10 ( $\pm$  3 days)
- **Visit 4:** Week 6 ( $\pm$  5 days)
- **Visit 5:** Week 12 ( $\pm$  7 days)
- **Visit 6:** Week 24 ( $\pm$  14 days)
- **Visit 7:** Week 36 ( $\pm$  14 days)
- **Visit 8:** Week 52 ( $\pm$  28 days)
- **Visit 9:** Week 104 ( $\pm$  56 days)

The Study Flowchart and Follow-Up Assessments table (Table 3) outline the study procedures and timelines.

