## 9. PROTOCOL

### 9.1 Study Design

This is a non-inferiority, prospective, double blinded, multi-center, randomized, controlled, adaptive study design with enrollment of 82 randomized subjects at up to 13 study sites. Study duration will be until the last subject enrolled reaches 104 weeks post-operative.

The study will be comprised of two parts:

**Part I:** Part I will require all Investigators perform 1 to 3 procedures using the Quantum 2 Controller plus Paragon T2 ICW Wand or the WEREWOLF Controller plus FLOW 50 Wand. Investigators must be qualified by training to perform procedures prior to use of either study device. This purpose of Part I will be to minimize variability with the recommended

directions for use established in the instructions for use (IFU). Part I subjects will be followed per protocol follow-up requirements, and will be included in the safety population only. These subjects will be additive (to the safety population) to the 82 randomized subjects planned as part of the primary evaluation in Part II.

**Part II:** Part II 82 randomized subjects. Each Investigator may initiate enrollment of subjects in this part of the study following completion of Part I requirements.

The Part II study implements a randomized adaptive study design, whereby an interim analysis will be conducted for sample size re-assessment. There is no intention of reducing the sample size as a result of this interim analysis; however, the sample size may be increased to either establish the non-inferiority and/or may be increased sufficiently to establish superiority depending on the results of the interim analysis.

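### The TEAE definition starts at the first randomised treatment, so, read literally, no event in the never-randomised Part I subjects can be a TEAE

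*Protocol*

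**What the plan says.** Protocol section 12.7.6.1 defines TEAEs as "events with an onset on or after the first randomized treatment". It then asks for TEAE tables by treatment group, System Organ Class and preferred term, with further tables by severity grade and by relationship to the device. The same section adds that "separate summaries of Serious Adverse Events will also be presented" and that "AEs/ADEs will also be tabulated versus worst severity and worst relationship to the intervention". It closes with a rule that uses a different starting point: "AEs recorded before administration of intervention will only be presented in listings".

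Section 12.6.3 defines the Safety population as everyone who received the device or treatment, and states: "This population includes the subjects from both Parts I and II of the study". Section 12.7.6 uses that population for safety outcomes and summarises by device/treatment group.

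Section 9.1 describes Part I. It says "Part I will require all Investigators perform 1 to 3 procedures" with one of the RF systems, and that "Part I subjects will be followed per protocol follow-up requirements, and will be included in the safety population only". These subjects are additional to the 82 randomised in Part II. Section 17.1 repeats that they are analysed for safety alone. Randomisation is described only for Part II (sections 9.1 and 12.3).

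**The concern.** The definition and the population do not fit together. A Part I subject receives a study device but has no randomised treatment, so there is no date from which an event could count as treatment-emergent. Safety is the only analytic use the protocol makes of these subjects, yet the definition that governs the main adverse event tables leaves them out.

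If the definition is programmed as written, the TEAE tables cover the randomised subjects only, while their stated population covers both parts. A reader of the report would take the tables to describe everyone treated with the RF device. They would omit the investigators' first study cases, the group for which Part I was set up.

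**Working it through.** This is mainly a reading of definitions; the arithmetic shows only how many subjects are involved.

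**Step 1: the sections side by side.**
- Who is analysed: all treated subjects, Parts I and II (12.6.3, 12.7.6).
- Who is randomised: Part II only (9.1, 12.3).
- When a TEAE can start: from the first randomised treatment (12.7.6.1).
- When adverse event reporting starts: from any study treatment or randomisation (13.3.1). This covers Part I.
- What is confined to listings: events before the intervention is given (closing rule of 12.7.6.1). This starting point exists for every treated subject.

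Of the three starting points, only the TEAE definition cannot be evaluated for a Part I subject. The other two suggest that treatment itself is the intended anchor. They do not strictly contradict the definition, because TEAEs may be a narrower set than the events collected.

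**Step 2: what is lost and what is kept.** Lost on the literal wording are all Part I events in the TEAE tables by class and term, severity and relationship. Kept are collection of the events (13.3.1) and subject listings (12.5.4 lists all collected data). They may also be kept in the serious adverse event summaries, which are not expressly limited to TEAEs.

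**Step 3: the randomised part of the count.** The plan states 82 randomised, 41 per group, from 70 completers and 15% discontinuation. Check: 70 / 0.85 = 82.35, so the stated figure is reproduced to within rounding. Nothing below depends on that rounding.

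**Step 4: size of Part I.** Let m be the number of investigators and c the cases per investigator (1 to 3, section 9.1). Then k = m × c. Assume all 82 randomised subjects are treated as assigned.
- Share of RF-treated subjects = k / (41 + k)
- Share of the Safety population = k / (82 + k)

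The protocol does not give m. It plans "enrollment of 82 randomized subjects at up to 13 study sites" (section 6), so m = 13 is an assumption of one investigator at each of the maximum number of sites.
- m = 13: k = 13 to 39. RF share 13/54 = 24.1% to 39/80 = 48.8%. Safety share 13/95 = 13.7% to 39/121 = 32.2%.
- m = 6: k = 6 to 18. RF share 6/47 = 12.8% to 18/59 = 30.5%. Safety share 6/88 = 6.8% to 18/100 = 18.0%.
- m = 20 (more than one investigator at some sites): k = 20 to 60. RF share 20/61 = 32.8% to 60/101 = 59.4%. Safety share 20/102 = 19.6% to 60/142 = 42.3%.

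These are counts of subjects whose events cannot be TEAEs under the literal wording. They are not effects on event rates, for which the protocol gives no figures.

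**The case against.** The strongest reply is that the intention is plain. The Safety population expressly includes Part I, section 17.1 says those subjects are there for safety, reporting starts at any study treatment, and the listing rule refers to the intervention. A sensible programmer would use the treatment date. Each subject has one study procedure, so nothing changes for Part II. On this view the problem is one misplaced word, and the statistical analysis plan can settle it before database lock (section 12.7). Most of this stands, and it is why the point is minor. It does not remove the point: the protocol states this definition rather than leaving it open, so an analysis plan that follows it inherits the fault and one that departs from it disagrees with the protocol.

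A reader might infer several stronger things that the documents do not support.
- *Part I subjects will be pooled into the RF column.* Section 12.1 defines the two groups by randomisation, so Part I subjects belong to neither. No sentence excludes pooling, but none prescribes it, and table layout is ordinary analysis-plan content.
- *The RF event rate will be diluted.* That needs Part I in the RF denominator, which is the same inference, and an event rate that would have to be invented.
- *Baseline tables share the fault.* In section 12.7.2 the reference to the safety population may attach to the by-subject listing alone.
- *Serious events in Part I go unreported.* Section 13.3.3 does refer to hospitalisation after randomisation, but the general definition in 13.1.3 has no such limit, so reporting does not depend on that wording.
- *The tables of 12.7.6.1 must disagree with one another.* The AE/ADE sentences may be counting rules rather than separate, wider tables.

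**Conclusion.** The TEAE definition is wrong as written for a Safety population that includes Part I. Literally applied, it excludes every Part I event from the TEAE tables. The fault lies in classification and tabulation, not in data capture. No safety hypothesis is tested (sections 12.7 and 12.7.6), and no efficacy result changes.

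With 13 investigators assumed, the excluded subjects would be about a quarter to a half of all those treated with RF. Because 13 is the ceiling on sites and the number of investigators is not given, this is an illustration of scale and not an estimate. The effect on reported event rates cannot be given. Severity: minor.

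**What to change.** Define a TEAE as an event with onset on or after administration of the study intervention, for every treated subject in Part I or Part II. This is the starting point the section already uses for its listing rule, so the two would then meet without a gap.

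Do not use the start of the procedure as the anchor. Under sections 11.1.1 and 11.3.2.1, diagnostic arthroscopy comes before randomisation and the assigned debridement. An event during that arthroscopy would then be a TEAE, while the listing rule sends it to listings only.

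As an accompanying step, show Part I RF subjects in a separate column and state that the RF versus control safety display uses randomised Part II subjects only. The summaries are by group on a population that mixes both parts, so saying this removes any doubt.

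The cost is one phrase and one table column, in the protocol or in the analysis plan before database lock. No new data are needed.
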